#### 8.1.4 Administration of Saracatinib

Saracatinib will be administered orally, once daily, every day, until the patient comes off study. The tablets can be taken at any time of the day, with or without food. See sections 4.5, 4.6 and 4.7 for a list of medications and food products that should be avoided while on study.

Each cycle will consist of 28 days, but there will be no breaks between cycles.

Should emesis occur after swallowing the saracatinib tablet, an additional dose is not to be given. The only exception is when emesis occurs immediately after swallowing the saracatinib tablet, and a fully intact, regurgitated, tablet is recovered.

For patients who cannot swallow tablets, the following guideline must be followed to crush either the 50 mg or the 125 mg tablets.

- Ensure that the crusher is clean and thoroughly dry (Ezy Dose Tablet Crusher with Pill Container, stock number 71091 from Apothecary Products Inc, Minneapolis or equivalent).
- Place the crusher on its base on a flat surface, insert the tablet and screw down the crusher cap to crush the tablet.
- Rotate the crusher cap repeatedly backwards and forwards (about one quarter turn in each direction).
- Unscrew the cap by about one half turn, then tap the crusher sharply on the table, to redistribute the powder. Do not shake or invert the crusher.

- Repeat the crushing process until a fine powder has been produced. Note that the pink coating on the tablet may remain as flakes. This is not critical. As long as the inside of the tablet has been ground to a fine powder, this is sufficient.
- Unscrew the crusher cap and transfer the powder into an appropriate glass container. If any significant amounts of tablet remain stuck to the crusher, these should be scraped or tapped out and added to the container.
- Add 50 ml of water to the crushed tablet in the glass container and drink immediately.
- Clean and dry the tablet crusher in preparation for the next dose.

Should emesis occur after swallowing the saracatinib suspension, an additional dose is not to be given, since it is impossible to estimate the amount of saracatinib that has been delivered.

For patients who require administration of saracatinib through a gastrostomy tube, the following guideline must be followed.

- Note: The elapsed time from the first addition of water to the crushed tablet to the administration of rinse through the gastrostomy tube should not exceed 4 hours.
- Stir the water and tablet powder together for 15 seconds. Then promptly draw the suspension into the syringe.
- Administer through the gastrostomy tube.
- Add 50 ml water to the glass container as a rinse, stir for 15 seconds and draw into the syringe.
- Administer through the gastrostomy tube.
- Clean and dry the tablet crusher in preparation for the next dose.
- Rinse the syringe with water.

#### 8.1.5 Known toxicities of Saracatinib

For further information regarding saracatinib, please refer to the Investigator's Brochure.

The following events are to be regarded as expected for regulatory reporting purposes:

General symptoms	flu-like symptoms - including fever, fatigue, musculoskeletal pain, headache fatigue
------------------	--

Hematological symptoms	mild bleeding (such as epistaxis) mild bruising (such as bruising at a venipuncture site)
Respiratory symptoms	pneumonitis
Gastrointestinal symptoms	nausea vomiting diarrhea
Skin symptoms	rash, generally papular
Laboratory findings	decrease in neutrophil count including neutropenia decrease in platelet count including thrombocytopenia increase in serum creatinine increase in serum C-reactive protein positive protein on urinalysis positive heme or RBCs on urinalysis

## 8.2 Placebo

Placebo tablets contain mannitol, microcrystalline cellulose, sodium starch glycolate and magnesium stearate. The drug substance is substituted with an equal quantity of mannitol. Placebo tablets are provided to match the active tablets in size, shape and color. The tablets should be stored at room temperature in the pack provided. The expiration date will be listed on the product label. For further information, investigators should refer to the investigational product label. Placebo tablets will be prepared by AstraZeneca and supplied by a third party vendor to the hospital pharmacy for subsequent distribution to the patient. The same instructions as described above (see Section 8.1.4), should be used for patients who are not able to swallow the tablets whole, or who require administration through a gastrostomy tube.

Since this is a double-blinded, placebo-controlled study, patients must refrain from taking certain medications and food products (see Sections 4.5, 4.6 and 4.7).

## 8.3 Drug Ordering

See Operations Manual for details of Drug supply/ordering.

### 8.3.1 Initial Supply

The investigational drug will be supplied by AstraZeneca and will be distributed to individual sites by a third party vendor.

Initial drug supply is provided to maintain a minimum inventory at the site to avoid delays in starting patient treatment.

The drug order supply form must be faxed or emailed to SARC. Upon confirmation that SARC has received all necessary regulatory documents, the contract is fully executed, and the site initiation meeting completed, SARC will authorize the initial drug supply shipment.

Requests should be submitted at least 5-7 business days before the expected delivery date. Deliveries will be made Tuesday through Friday.

Please complete the Saracatinib (AZD0530) Drug Supply Form (see Appendix D for drug supply form). Fax or email the form to SARC Operations Office:

SARC Research Project Manager  
SARC operations office [contact] or  
Email: [contact]

### 8.3.2 Re-Supply

Re-supply requests can be obtained by completing the saracatinib Drug Supply Form (see Appendix D for drug supply form). Fax or email the form to SARC as above.

Requests should be submitted at least 5-7 business days before the expected delivery date. Deliveries will be made Tuesday through Friday.

## 8.4 Investigational Product Records at Investigational Site(s)

It is the responsibility of the Investigator to ensure that a current record of investigational product disposition is maintained at each study site where investigational product is inventoried and disposed. Records or logs must comply with applicable regulations and guidelines, and should include:

- Amount received and placed in storage area.
- Amount currently in storage area.
- Label ID number or batch number and use date or expiry date.
- Dates and initials of person responsible for each investigational product inventory entry/movement.
- Amount dispensed to and returned by each subject, including unique subject identifiers.
- Amount transferred to another area/site for dispensing or storage.
- Non-study disposition (e.g., lost, wasted, broken).
- Amount destroyed at study site.

Investigational product dispensing record/inventory logs and copies of signed packing lists must be maintained at the investigational site. Batch numbers for saracatinib must be recorded in the drug accountability records.

## **8.5 Destruction of Investigational Product**

It is the Institutional Principal Investigator's responsibility to ensure that arrangements have been made for disposal and that procedures for proper disposal have been established according to applicable regulations, guidelines, and institutional procedures. Appropriate records of the disposal must be maintained. Unused drug and empty bottles will not be returned to AstraZeneca.

A copy of the institutional drug disposal policy should be sent to SARC for retention in the Trial Master File.

## 10 Appendices

### Appendix A – On Study Evaluations

Study Month	screening	pre dose	day 1	week 1(g)	week 3-4 (g)	week 6-8 (h)	week 9 (h)
Interim History	X	X (d)		X (d)	X	X	X (d)
Physical Examination	X	X (d)		X (d)	X	X	X (d)
Weight, Height, Vital Signs	X	X (d)		X (d)	X	X	X (d)
Laboratory Tests (a, f)	X	X (d)		X (d)	X	X	X (d)
Thoracic CT (b)	X				X	X	
Bone Scan	X						
EKG	X						
Echocardiogram or MUGA	X						
Creatinine Clearance (c)	X						
Pregnancy Test	X						
ECOG Score	X						
Begin Oral Therapy			X	----->			

Study Month	3 Mo Cycle 3 (h)	4 Mo Cycle 4 (h)	5 Mo Cycle 5 (h)	6 Mo Cycle 6 (h)	7 Mo Cycle 7 (h)	8 Mo Cycle 8 (h)	9 Mo Cycle 9 (h)	10 Mo Cycle 10 (h)	11 Mo Cycle 11 (h)	12 Mo Cycle 12
Interim History	X	X (d)	X (d)	X	X (d)	X (d)	X	X (d)	X (d)	X
Physical Examination	X	X (d)	X (d)	X	X (d)	X (d)	X	X (d)	X (d)	X
Weight, Height, Vital Signs	X	X (d)	X (d)	X	X (d)	X (d)	X	X (d)	X (d)	X
Laboratory Tests (a)	X	X (d)	X (d)	X	X (d)	X (d)	X	X (d)	X (d)	X
Thoracic CT (b)	X			X			X			X
EKG	X									
Continue Oral Therapy	X	----->								

### Suggested Follow-up

Study Month	End of Trmt 13 mo	15 mo	18 mo	21 mo	24 mo	30 mo	36 mo
Interim History	X	X (d)	X	X (d)	X	X (d)	X
Physical Examination	X	X (d)	X	X (d)	X	X (d)	X
Weight, Height, Vital Signs	X	X (d)	X	X (d)	X	X (d)	X
Laboratory Tests	X		X		X		X
Thoracic CT	X		X		X		X
Bone Scan	X						
EKG	X						
End Oral Therapy	X (e)						

- White blood cell count with differential, hemoglobin, hematocrit, platelet count, sodium, potassium, chloride, bicarbonate, blood urea nitrogen, creatinine, glucose, calcium, magnesium, phosphorus, ALT, AST, total bilirubin, alkaline phosphatase, lactate dehydrogenase, total protein, albumin
- Thoracic CT scan must be performed at a slice thickness of 5 mm or less
- For patients with serum creatinine >1.5
- These visits do not need to be performed at the study center, however, documentation of the required items must be sent to the study center as soon as they are available
- Saracatinib or placebo will be discontinued after 13 cycles (364 days) of therapy
- Prior to beginning oral therapy, treating physicians should obtain a full work-up to evaluate low or borderline low levels of phosphorus. (See section 3.3.3)
- Treatment evaluations/procedures should be performed within +/- 3 days.
- Treatment evaluations/procedures should be performed within +/- 3 days.

**Appendix B – SARC 012 Patient Pill diary**

PATIENT INITIALS: \_\_\_\_\_ SUBJECT UNIQUE STUDY # \_\_\_\_\_

Please complete this chart each time you take study drug. You may take the study drug at any time of the day with or without food. Please contact the study staff before changing the dose of the study drug. Once completed, please return this chart to the study staff.

**Study Drug Dose: 175 mg daily, 125 mg daily, or 100 mg daily**

*Note: Should vomiting occur after swallowing the saracatinib tablet, an additional dose is not to be taken. The only exception is when vomiting occurs immediately after swallowing the Saracatinib tablet, and a fully intact, regurgitated tablet is recovered. The following food products must not be taken while the patient is on study: grapefruits, grapefruit juice, star fruits, Seville oranges (also known as Chinese Bitter Oranges) and Seville orange marmalade.*

Day	Date	Time	AM / PM	Dose of Study Drug	Comments
Day 1	/ /			mg	
Day 2	/ /			mg	
Day 3	/ /			mg	
Day 4	/ /			mg	
Day 5	/ /			mg	
Day 6	/ /			mg	
Day 7	/ /			mg	
Day 8	/ /			mg	
Day 9	/ /			mg	
Day 10	/ /			mg	
Day 11	/ /			mg	
Day 12	/ /			mg	
Day 13	/ /			mg	
Day 14	/ /			mg	
Day 15	/ /			mg	
Day 16	/ /			mg	
Day 17	/ /			mg	
Day 18	/ /			mg	
Day 19	/ /			mg	
Day 20	/ /			mg	
Day 21	/ /			mg	
Day 22	/ /			mg	
Day 23	/ /			mg	
Day 24	/ /			mg	
Day 25	/ /			mg	
Day 26	/ /			mg	
Day 27	/ /			mg	
Day 28	/ /			mg	

Patient Signature \_\_\_\_\_ Date \_\_\_\_\_

**To be completed by Study Staff:** Drug Bottle(s) Return Date: \_\_\_\_\_

# of 125 mg tablets dispensed \_\_\_\_\_ / returned \_\_\_\_\_

# of 50 mg tablets dispensed \_\_\_\_\_ / returned \_\_\_\_\_

Study Staff Signature \_\_\_\_\_ Date \_\_\_\_\_

**Investigator:**

**Site:**

Study Title: A Randomized, Double-Blinded, Placebo-Controlled, Multi-Institutional, Phase II.5 Study of Saracatinib (AZD0530), a Selective Src Kinase Inhibitor, In Patients with Recurrent Osteosarcoma Localized to the Lung

**Subject Study ID:** \_\_\_\_\_ **Subject Study Initials:** \_\_\_\_\_

**Type of Report:**  **Initial**     **Follow-up #** \_\_\_\_\_

Please list all AEs by unique term and CTCAE v3.0 grade. Use additional cover sheets if necessary:

AE term 1:	Grade	Causality to study drug?	Yes / No
		Causality to other medication?	Yes / No
		Causality to study procedure?	Yes / No
		Causality to study drug?	Yes / No
AE term 2:	Grade	Causality to other medication?	Yes / No
		Causality to study procedure?	Yes / No
		Causality to study drug?	Yes / No
AE term 3:	Grade	Causality to other medication?	Yes / No
		Causality to study procedure?	Yes / No
		Causality to study drug?	Yes / No
AE term 4:	Grade	Causality to other medication?	Yes / No
		Causality to study procedure?	Yes / No
		Causality to study drug?	Yes / No

**Is any AE listed above fatal or life-threatening?**     **Yes**     **No**

Photocopies of supportive documents; attach if relevant, tick those attached

**Lab report(s)**     **Autopsy report**     **Other: details** \_\_\_\_\_

All serious adverse events will be reported and documented on MedWatch Form FDA 3500 A as follows:

- If more than one SAE is listed each event should be numbered.
- Investigator must designate causality as YES or NO for each SAE in the “Describe event” narrative section of the MedWatch form. If there is any possibility that the SAE is related to study drug, then designate Yes for causality. If there is clearly no possibility that the SAE is related to study drug, then designate No for causality.
- If causality is due to other medication or study procedure, please provide a clear description and reasoning in the narrative section of the MedWatch form.
- The date the site notified SARC and AstraZeneca of the SAE must be specified in the “Describe event” narrative section of the MedWatch form. Initial and follow-up MedWatch reports should be numbered either in the narrative section or in section G.7 of the MedWatch form.

**Appendix D – Drug Supply Form**

**ASTRAZENECA**  
**Saracatinib (AZD0530) DRUG SUPPLY FORM**  
**FOR INVESTIGATOR SPONSORED STUDY - SARC 012 (D8180C00039)**

**REQUEST FOR DRUG SHIPMENT TO SITE (AZ)**

AZ Protocol Number D8180C00039	Group Protocol Number SARC012	Site Name (as Institution) and Number:	
Investigator Name:  [name] Reach Destination By: DD/MM/YYYY (Deliveries are not made on Monday: allow five (5) working days for resupply)	
Investigator Address:  Telephone Number:		Pharmacy Address - Where Supplies Should Be Delivered: (If Different From Investigator Address and Contact)  Pharmacy Contact:  Telephone Number:  E-mail (if available):	
DRUG REQUIRED:			
Study Drug:	Saracatinib (AZD0530)	Saracatinib (AZD0530)	
Strength/ Dose Form:	50mg tablets/ 35 per bottle	125mg tablets/35 per bottle	
QUANTITY NEEDED	No. of bottles:	No. of bottles:	
Study Drug:	Placebo Saracatinib (AZD0530)	Placebo Saracatinib (AZD0530)	
Strength/ Dose Form:	50mg tablets/ 35 per bottle	125mg tablets/35 per bottle	
QUANTITY NEEDED	No. of bottles:	No. of bottles:	
Comments:			

## **Appendix E – Local MD Guidelines**

For patients enrolled on this study, evaluations must be administered at the study site for the pre-treatment evaluation and for the 3, 6, 9, and 13month visits (cycle 3, 6, 9 and end of cycle 13). For all other study evaluations, the investigator may determine in the best interest of the patient that those evaluations may be safely conducted at a local, competent, referring oncologist's office. The institutional principal investigator is responsible for the timely and accurate reporting of data to the SARC Operations Center.

- SARC institutional PI communication with the outside physician is required prior to the patient returning to the local physician. This will be documented in the patient record.
- A letter to the local physician outlining the patient's participation in a clinical trial will request local physician agreement to supervise the patient's care. (Sample letter- Appendix F).
- Protocol required evaluations outside the consortium site will be documented by telephone, fax, or e-mail. Fax or e-mail will be dated and signed by the SARC institutional PI, indicating that they have reviewed it.
- Documentation to be provided by the local physician will include all drug administration records, progress notes, reports of protocol required laboratory and diagnostic studies and documentation of any hospitalizations.
- SARC institutional PI is responsible for all adverse event reporting, timely and accurate submission of serious adverse events reporting as outlined in Section 7.3

## Appendix F – Local MD Agreement Letter

Date

Dear Doctor,

“**Name**” is a mutual patient of ours with sarcoma. He/she is participating in a multi-center randomized trial of Saracatinib (AZD0530). The study involves continuous study drug administration with interval lab studies, physical exams and CT scans. The cycle is repeated every 28 days, without any breaks between cycles. We are inquiring as to your willingness to supervise a portion of this patient’s care while on the trial.

“**Name**” would like to be evaluated at XXXX and obtain the lab studies at your office. In order for this to be done, we will need the following:

- confirmation of your willingness to obtain lab studies
- ability to obtain thoracic CT scans and relay reports and images, if required, to the study center
- agreement to report all serious adverse events within 24 hours
- agreement to discuss and obtain approval prior to any change in drug dose and/or schedule
- a copy of your lab’s certification
- a fax copy of the documented, dictated or handwritten, findings of patient visits, record of study doses and administration, lab results and documentation of any hospitalizations

If you agree to the above, we would ask you to sign and return this letter as confirmation that you will comply with the items as outlined above.

By signing below, I agree to perform all tests and evaluations as noted above, and fax all documentation to **name and fax number**.

---

Signature date

A copy of the abstract, study schema, and study calendar are included with this letter. Should you have any questions or need additional information, please do not hesitate to contact: **Name and Contact Information**

Sincerely,

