In patients with advanced cancer, the pharmacokinetic profile of saracatinib, at doses between 50 mg and 250 mg, was generally similar to that observed in healthy volunteers. However, there was a tendency for patients to have slightly higher plasma concentrations. Exposure to saracatinib increased in an apparently dose-proportional manner after a single dose. Accumulation with once daily dosing was 4-6 fold across the dose levels. Steady state was achieved after 10 days, at which point the increase in exposure with the dose was proportional, up to the 175mg dose. The table below summarizes the results of this two-part study.

Dose (mg/day)	Demographics and drug exposure				Steady State Pharmacokinetics (geometric mean)			
	N	Time on Treatment (days)	Age (years)	Weight (kg)	N	C ss,max (ng/mL)	AUC ss (ng.h/mL)	CL/F (L/h)
Part B								
50	16	9-51	40-72	49-92	11	95	1597	31.3
125	16	22-210	42-75	34-88	15	247	3691	34
175	19	7-45	20-71	35-110	16	444	7588	23.2
Part A								
175	5	11-65	49-73	37-98	4	484	7911	22.2
250	7	6-61	23-70	52-88	2	493, 1090	9070, 198000	28.7, 12.6

N Number of patients providing data for the particular endpoint

Css,max Maximum plasma concentrations at steady state

AUCss Area under the plasma concentration curve during the dosing interval at steady state

CL/F Oral drug clearance

To determine saracatinib levels in tumors, tissue was homogenized, subjected to solvent extraction and analyzed by high performance liquid chromatography with mass spectrometric detection. At steady state, the concentrations of saracatinib in tumor tissue were approximately 70 times greater than in plasma, in human patients.

Saracatinib is an inhibitor of CYP3A4 in vitro. The relevance of this finding was examined in a clinical study using midazolam, a recognized substrate of CYP3A4. Saracatinib, at a dose of 125 mg/day, resulted in an average increase in the plasma AUC of midazolam of 2.7-fold. This observation classifies saracatinib as a moderate inhibitor of CYP3A4 and suggests the possibility that it could affect the exposure and effects of co-administered drugs. Medications that are contra-indicated (see Section 4.5) and recommendations regarding the use of drugs known to be sensitive to inhibition of this enzyme are included in this protocol (see Section 4.6). A list of contra-indicated foods is also provided (see Section 4.7).

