### 3.3.2 Dose Reduction of Oral Therapy

If a patient experiences any of the toxicities defined in section 3.3.1, or another unacceptable toxicity occurs, and the investigator considers that the event is related to the study drug, oral therapy will be stopped for a maximum of 21 days, and supportive therapy will be administered as required. If the toxicity resolves or reverts to a CTCAEv3 grade 0 or grade 1 or to the baseline (pre-study) grade within 21 days of onset, oral therapy will be restarted at a lower dose as follows:

If a patient is currently taking 175 mg, the lower dose will be 125 mg.

If a patient is currently taking 125 mg, the lower dose will be 100 mg.

A maximum of two dose decreases, for any individual patient, can be made during the study period, down to the lowest dose of 100 mg of saracatinib or placebo.

If a patient experiences any of the toxicities defined in Section 3.3.1, or another unacceptable toxicity occurs, while taking 100 mg, then the patient must be withdrawn from the study. For all patients who experience any of the toxicities defined in Section 3.3.1, or another unacceptable toxicity occurs during the study, if the toxicity does not resolve to CTCAEv3 grade 0 or grade 1 or to the baseline (pre-study) grade within 21 days of onset, then the patient must be withdrawn from the study. Patients will continue to be monitored until the toxicity has resolved.

Patients will continue to be monitored for overall survival for the duration of the study. If patients have toxicity that requires their removal from the study prior to ascertainment of disease progression, then these patients will be considered treatment failures in the time to treatment failure analysis and the duration of total treatment will be included in the time to treatment failure. However, for the progression free survival analysis, withdrawals due to toxicity will be censored, as the subject has not progressed.

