24 months	history, physical, vital signs, laboratory tests thoracic CT
30 months	history, physical, vital signs *
36 months	history, physical, vital signs, laboratory tests thoracic CT

Laboratory tests are as follows:

- white blood cell count with differential
- hemoglobin and hematocrit
- platelet count
- sodium, potassium, chloride, bicarbonate, blood urea nitrogen, creatinine, glucose
- calcium, magnesium, phosphorus
- ALT, AST, total bilirubin,
- alkaline phosphatase, lactate dehydrogenase, total protein, albumin

\* At the discretion of the treating physician, these visits do not need to be performed at the study center. However, a document containing the interim history, physical examination, weight and height, vital signs, laboratory tests, and CT scan results when appropriate, must be sent to the treating physician at the study center as soon as they are available.

\*\* The purpose of the two additional thoracic CT scans is to monitor for interstitial lung disease, which has been seen in 2% of patients taking saracatinib. If there is any suspicion of interstitial lung disease on any CT scan, the patient must undergo high-resolution CT imaging to exclude interstitial lung disease. Any evidence of interstitial lung disease will lead to removal of the patient from the study (defined in the Exclusion Criteria in Section 2.1.2.f). The suggested parameters for the high-resolution thoracic CT scan are as follows: position (supine), slice thickness ( $\leq 1.25$  mm), slice spacing (10 mm), start location (10 mm below the apices), end location (10 mm above the costophrenic angles).

\*\*\* Previous studies have not demonstrated prolonged QTc intervals in patients treated with saracatinib. A 12-lead EKG should be obtained after the patient has rested in a supine position for at least five minutes. The treating physician should review the EKG. Any abnormality of clinical significance should result in medical management of the patient as clinically indicated. The abnormality should be reported as an adverse event or a serious adverse event (see Section 7.2).

\*\*\*\* Saracatinib or placebo will be discontinued after thirteen 28-day cycles (364 days) of therapy.

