### **4.4 Respiratory Care**

As described previously (Section 1.2.8), four adult patients developed pulmonary adverse events, possibly due to concurrent treatment with saracatinib. The development of any pulmonary symptom, no matter how minimal it may be, must be investigated immediately. Patients who have cough or slight discomfort in association with an upper respiratory infection may be monitored clinically, if the symptoms resolve or improve within a period of seven days.

Any patient who develops a pulmonary symptom, or has worsening of symptoms, will undergo thoracic CT as soon as possible. Pulmonary symptoms include, but are not limited to the following: cough, dyspnea, pain, hemoptysis, or oxygen saturation <94%. Oral therapy will be stopped immediately and the algorithm below should be followed.

If any of the following (cough, dyspnea, new pulmonary radiologic abnormality) occur or worsen while on study and cannot categorically be clinically ascribed to a cause other than saracatinib dosing, then

Interrupt saracatinib dosing

Perform a \*CT scan of the thorax  
Consider \*HRCT if necessary to rule out interstitial lung disease  
(defined as bilateral, diffuse, parenchymal lung disease)

CT scan of the thorax  
**DOES NOT** show interstitial lung disease  
(bilateral, diffuse, parenchymal lung disease)

CT scan of the thorax  
**DOES** show interstitial lung disease  
(bilateral, diffuse, parenchymal lung disease)

Consider re-commencing saracatinib dosing

Permanently discontinue saracatinib dosing

Begin appropriate management  
(Consider initiation of steroid therapy if non-drug related etiologies have been excluded)  
(Referral to a pulmonologist is recommended)

\*CT scan of thorax to be performed with slice thickness  $\leq 5$ mm

\*HRCT scan recommended parameters:

position	supine
slice thickness	$\leq 1.25$ mm
slice spacing	10 mm
start location	10 mm below the apices
end location	10 mm above costophrenic angles

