### 7.2.2 Recording Procedures for All Adverse Events

All observed or volunteered adverse events, regardless of treatment group or suspected causal relationship to study drug, will be recorded as an Adverse Event in the case report forms at each study visit. Adverse events should be collected from the time the patient provides informed consent to participate in the study until 30 days after the last dose of study medication. Events involving adverse drug reactions, illnesses with onset during the study, or exacerbation of pre-existing illnesses should be recorded. Objective test findings (e.g., abnormal laboratory test results) that result in a change in study drug dosage should also be recorded.

All AEs will be recorded on the CRFs provided. A description of the event, including its date of onset and resolution, whether it constitutes a SAE or not, the date it became serious, seriousness criteria (e.g. fatal, life-threatening, hospitalization, disability, congenital anomalies), any action taken (e.g., changes to study treatment, other treatment given and follow-up tests) and outcome should be provided along with the Investigator’s assessment of causality to the study drug, study medication and study procedure.

It will be left to the treating physician’s clinical judgment whether or not an adverse event is of sufficient severity to require that the subject should be removed from treatment. A subject may also voluntarily withdraw from treatment due to what she/he perceives as an intolerable adverse event. If either of these occurs, the subject will be given appropriate care under medical supervision until the symptoms cease or until the condition becomes stable.

The severity of toxicities will be graded in accordance with the Common Terminology Criteria for Adverse Events Version 3.0 (<http://ctep.cancer.gov/forms/CTCAEv3.pdf>). A link to CTCAE v3 is also provided in the study database in the adverse event CRFs.

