## 8 Pharmaceutical Information

### 8.1 Saracatinib (AZD0530)

#### 8.1.1 Chemical Information

Chemical Name : *N*-(5-Chloro-1,3-benzodioxol-4-yl)-7-[2-(4-methylpiperazin-1-yl)ethoxy]-5-(tetrahydro-2*H*-pyran-4-yloxy)quinazolin-4-amine

Chemical Structure :

Molecular Formula : C27H32ClN5O5

Molecular Weight : 542.04 as free base

Half-life 40 hours in humans

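### The sample local-physician letter (Appendix F) requires approval before any dosing change and has no safety exception; read literally, this conflicts with the immediate stop for pulmonary symptoms in section 4.4 (small risk, one-line fix)

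*Combined protocol and SAP*

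**What the plan says.** Appendix F is the letter a local physician signs before supervising part of a patient's care. One item is "agreement to discuss and obtain approval prior to any change in drug dose and/or schedule". The letter describes dosing as continuous, with no breaks between 28-day cycles. It lists the abstract, the schema and the study calendar as enclosures, and section 4.4 is not listed.

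Section 4.4 sets the rule for pulmonary symptoms: "Oral therapy will be stopped immediately and the algorithm below should be followed". Its algorithm begins with interruption of dosing, then CT. Two limits apply. "Patients who have cough or slight discomfort in association with an upper respiratory infection may be monitored clinically", provided they resolve or improve within seven days. The algorithm also covers only events that cannot be firmly put down to a cause other than saracatinib.

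Section 3.4 explains why lungs are watched closely: "The purpose of the two additional thoracic CT scans is to monitor for interstitial lung disease, which has been seen in 2% of patients" (here, those on saracatinib). Section 3.4 and Appendix E allow visits other than pre-treatment and cycles 3, 6, 9 and 13 to be held at a local oncologist's office where the investigator judges this safe.

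**The concern.** A hold departs from a schedule that the letter calls continuous, and the clause covers any change. A local physician who follows the signed wording would therefore seek approval first and stop drug second, while section 4.4 wants the stop first. The letter may be the main dosing instruction that this physician holds. At stake is patient safety at the margin: one or more further doses in a patient with possible drug-related lung toxicity while a call goes unanswered. The randomized comparison is not touched.

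**Working it through.** The point is one of wording, and the plan gives no figure to reproduce for it. The first two steps compare texts; the last two give scale.

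**1. The two rules side by side.**

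- Section 4.4: new or worsening pulmonary symptom → stop → CT → consider restart, or discontinue permanently if interstitial lung disease (ILD) is seen. No approval step comes before the stop.
- Appendix F: any change in dose or schedule → discuss → approval → change. No exception is written.

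If a hold counts as a change in schedule, the order is reversed. If the clause covers only departures from the protocol, there is no conflict. The visible text does not say which is meant. Appendix E, which governs local care, gives no instruction on stopping drug.

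**2. Which visits may be local.** From week 1 to cycle 13 there are 4 early visits (weeks 1, 3-4, 6-8, 9) and 11 cycle visits (cycles 3 to 13), 15 in all. The sources differ on how many may be local:

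- Asterisks in section 3.4: 4 + 6 = 10.
- Mark (d) in Appendix A: 2 + 6 = 8.
- Text of section 3.4 and Appendix E: 15 − 4 = 11.

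The two visits that separate 10 from 8 are weeks 3-4 and 6-8, the CT visits added to monitor for ILD. Section 3.4 releases them from the study center; Appendix A does not. The letter does ask whether the local physician can obtain thoracic CT, but that could serve a symptom-driven or follow-up scan, so it does not settle the matter.

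**3. How often it could arise.** Inputs: 2% ILD (section 3.4) and 44 saracatinib patients (section 5.3).

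- Expected ILD cases: 44 × 0.02 = 0.88.
- Chance of at least one: 1 − 0.98^44 = 0.589, about 59%.

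Only cases first seen by a local physician matter here. With that share written as s, the expected number is 0.88 × s: 0 if s = 0, 0.44 if s = 0.5, and 0.88 if s = 1. The documents do not give s. Two things are left out: placebo patients who cross over to saracatinib, and pulmonary symptoms without ILD, which also trigger the stop at a rate not given.

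**4. What a delay costs.** Dosing is once daily, so a call answered before the next dose adds no drug. If a dose is taken while waiting, let R be the accumulation ratio. Assuming linear kinetics with simple one-compartment decline, the exposure still to come from the last steady-state dose onward is R dosing intervals' worth, and one more dose adds one interval's worth, a fraction 1/R. Section 1.2.7 reports for patients: "Accumulation with once daily dosing was 4-6 fold across the dose levels". That gives 1/6 = 17% to 1/4 = 25% per extra dose. The observed accumulation is used in preference to the half-life, because section 1.2.7 describes biphasic disposition.

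**The case against.** The strongest reply is that a stop ordered by section 4.4 is the protocol's own instruction, not a change to it. Lines of this kind usually exist to prevent unilateral dose adjustment; the pill diary in Appendix B gives patients a similar one. Appendix F is only a sample, and Appendix E requires documented contact between the institutional PI and the local physician before local care starts. Section 7.2.2 gives the treating physician discretion, in these words: "clinical judgment whether or not an adverse event is of sufficient severity to require that the subject should be removed from treatment". Patients start drug within six weeks of lung resection, so symptoms with a surgical cause are foreseeable and a call to the study center may help.

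Much of this stands, and it is why the risk is small. It does not close the gap. Section 7.2.2 concerns removal from treatment, and the treating physician there may be the one at the study center, as a footnote in section 3.4 uses the term. None of the safeguards says in visible text that the local physician may stop first. The enclosed schema and the Operations Manual are not available to this review and might say so.

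A reader might go further in three ways that the documents do not support:

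- That the letter forbids the safety stop. It does so only on one of two fair readings.
- That the early ILD scans will be done under local care. Section 3.4 and Appendix A conflict on this.
- That the letter equally reverses the toxicity holds in section 3.3. Those apply when "the investigator considers that the event is related to the study drug, oral therapy will be stopped for a maximum of 21 days", so they already wait on the investigator's attribution.

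**Conclusion.** The point holds as an ambiguity on a safety instruction, at the level of an optional improvement. The letter's approval clause has no safety exception, and on a literal reading it conflicts with the immediate stop in section 4.4. The conclusion rests on counting a hold as a change in schedule, which is fair given how the letter describes dosing, but not the only reading.

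The practical risk is small. Fewer than one ILD case is expected in the saracatinib arm at the 2% rate, an unknown share of such cases would first be seen locally, and a call answered the same day adds no drug. The 59% chance of at least one case describes the saracatinib arm as a whole; it does not measure harm from the letter. Sample size, endpoints and analysis are unaffected.

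**What to change.** Reword the item to: "agreement to discuss and obtain approval prior to any change in drug dose and/or schedule", *except that study drug may be stopped at once for patient safety, and must be stopped at once for pulmonary symptoms as in section 4.4, with the study site called the same day; restart and dose reduction need prior approval*. Enclose section 4.4 with the letter.

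The general permission matters. If pulmonary symptoms were the only exception, the letter would by implication bar an urgent local stop for life-threatening toxicity (section 3.7) or pregnancy (section 4.3). Keeping approval for restart and dose reduction preserves the study site's control of dosing.

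The cost is re-issuing one template letter, including to physicians who have already signed, and an occasional hold that the study site would not have ordered.
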